6.2 Exclusion Criteria

Potential trial patients will be excluded if at least one of the following exclusion criteria is present:

1. Patients with insomnia symptoms present longer than 90 days prior to Screening Visit
2. Based on the diagnostic interview, reported history (within 2 years) of other sleep disorders (e.g., chronic insomnia, circadian rhythm sleep disorders, restless legs syndrome (RLS), obstructive sleep apnea (OSA)), i.e., STOPBang (SBQ) questionnaire score ≥ 5 , International Restless Legs Scale score ≥ 16)
3. Based on the first polysomnographic screening night at Baseline 1, insomnia due to sleep apnea or periodic limb movement disorder (PLMD): OSA (Apnea Hypopnea Index of >5 events/ hour), PLMD (Periodic Limb Movement Index (PLMI) >15 events/ hour)
4. Rotating shift work with overnight shifts
5. History of psychiatric disorders within the last 6 months prior to Screening Visit according to the Structured Clinical Interview for DSM-5® Disorders – Clinician Version (SCID-5-CV)
6. History of sensitivity to any component of Neurexan®
7. Unwilling or unable to comply with all the requirements of the clinical trial protocol
8. Cognitive impairment (cut-off of 24 points in the Montreal Cognitive Assessment [MoCA]; Thomann, Berres et al. 2020) at Screening Visit
9. Any history of or current abuse of alcohol and/or amphetamines, benzodiazepines, cocaine, marijuana, methaqualone, methadone, opioids, propoxyphene, barbiturates, phencyclidine; or expected to take during trial participation (urine drug screening at Screening Visit and adaptation nights)
10. Current use of medication affecting sleep, i.e., antidepressants, antipsychotics, diuretics, blood pressure drugs, anti-dementia drugs (e.g., piracetam), herbal and homeopathic medicine, hormone preparations (e.g., thyroxine) with the exception of hormonal contraceptives
11. Use of Neurexan® within the last two weeks from Screening Visit
12. Non-pharmacological insomnia therapies (e.g., cognitive behavioral therapy within the last 6 months of Screening Visit, sleep restriction therapy, complementary and alternative therapies as meditation, Traditional Chinese Medicine, aromatherapy)
13. Excessive consumption of xanthine-containing beverages (more than 7 cups daily of coffee or tea or other beverages containing xanthines)
14. Use of nicotine during the last 6 months prior to Screening Visit
15. Participation in any interventional clinical study within the past 30 days prior to Screening Visit

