7.6 Concomitant Medications/ Treatment

7.6.1 Prohibited Medications/ Substances/ Treatments During the Trial

- Abuse of alcohol and/or use of amphetamines, benzodiazepines, cocaine, marijuana, methaqualone, methadone, opioids, propoxyphene, barbiturates, phencyclidine
- Use of nicotine
- Medication affecting sleep, i.e., antidepressants, antipsychotics, diuretics, blood pressure drugs, anti-dementia drugs (e.g., piracetam), herbal medicine, hormone and homeopathic preparations (e.g., thyroxine) with the exception of contraceptives
- Use of Neurexan® different than IMP
- Non-pharmacological insomnia therapies (i.e., cognitive behavioral therapy, sleep restriction therapy, complementary and alternative therapies as meditation, Traditional Chinese Medicine, aromatherapy)
- Excessive consumption of xanthine-containing beverages (more than 7 cups daily of coffee or tea or other beverages containing xanthines).

8. Trial Procedures

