11.3 Statistical Planning

A detailed methodology for summary and statistical analysis of the data collected in this trial will be documented in a Statistical Analysis Plan (SAP). This has to be finalized at the latest prior to database lock. This document may modify the plans outlined in the protocol; however, any major modification of the primary endpoint definition and/or its analysis would also be reflected in a protocol amendment to be submitted to the Competent Authorities and Independent Ethics Committee for endorsement.

All programming of tables, figures, listings and statistical analyses will be performed using the statistical software package SAS® version 9.4 or higher.

The statistical planning and evaluation of the trial will be carried out by a qualified biostatistician in accordance with the ICH guidelines and adequate biostatistical SOPs.

Definition of Baseline

The last available information at or prior to Baseline 2/ Day 0 collected before randomization and subsequent first IMP intake will be defined as baseline value. For PSG derived parameters the baseline is defined as the night from Day -1 to Day 0 (Baseline 2).

Subgroup Analyses

The following subgroups will be defined:

- Age
- Sex (female/ male)
- Neurexan® responder vs. non-responder
- Duration of short-term insomnia (≤ 1 month, > 1 month)
- Cortisol response influenced by hormonal contraceptives

Other subgroups may be specified in the SAP or during the Blind Data Review Meeting (BDRM).

Descriptive Analyses

All variables will be described by treatment group using descriptive statistics.

For continuous variables the number of observations (n), arithmetic mean, standard deviation (SD), minimum, median, 25%- 75%-quantile, maximum, 95% confidence interval (CI) (2-sided), and the number of missing data will be presented.

For categorical variables n, frequency and percentage, 95% CI (where applicable), and number of missing data will be presented.

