11.4.2 Secondary Efficacy

For all secondary variables, exploratory statistics comparing the 2 treatment groups will be performed. Difference from baseline will be used, as appropriate. Group comparisons of continuous numeric parameters will be tested using an ANCOVA including treatment, the stratification factor sex, and the baseline value of continuous numeric parameters as covariate; comparisons of dichotomous variables are specified by using the Fisher's Exact Test.

Secondary analyses on efficacy will be exploratory in nature without adjustment for multiplicity. All secondary analyses will be performed with two-sided hypotheses on superiority using a Type I error level of 5%.

Secondary efficacy variables are the following:

Polysomnography at Baseline 2 and Visit 2

- SOL
- WASO
- TST
- NWAK
- Latencies to S1, S2, S3, REM
- Arousal Index (Arl).

Biochemical parameters

- Resting state cortisol and other stress-related parameters in saliva
- Serum cortisol levels and other stress-related parameters in response to the stress induction by CPT
- Stress test induced inflammation parameters in blood serum.

Actigraphy

- Continuous in-home assessment of sleep
- Daytime activity.

Patient Questionnaires

- Subclinical Stress Symptom Questionnaire-25 (SSQ-25)
- Primary Appraisal Secondary Appraisal (PASA)
- Perceived Stress Scale-10 (PSS-10)
- Epworth Sleepiness Scale (ESS)
- Würzburg Fatigue Inventory (WEIMuS)
- Short Form-36 (SF-36v2)
- Insomnia Severity Index (ISI)
- Pittsburgh Sleep Quality Index (PSQI)
- Beck's Depression Inventory-II (BDI-II)
- Beck's Anxiety Inventory (BAI).

Sleep diary (adapted from DGSM) data: subjective SE, SOL, WASO, TST, NWAK

Continuous digital stress assessments

Neurexan® response

Exploratory Efficacy Variables

- EEG based vigilance fluctuations during resting state
- EEG based vigilance fluctuations during CPT
- EEG based asymmetry index during resting state
- EEG based vigilance fluctuations during CPT
- Regional changes in spectral characteristics of EEG during resting state
- Regional changes in spectral characteristics of EEG during CPT
- Cognitive performance in three attentional tasks

- PSG sleep parameters derived from the two adaptation nights at Baseline 1 and Visit 1.

Correlations between

- Changes in sleep parameters, stress parameters, and daytime performance
- Changes in sleep parameters, stress parameters, and inflammatory parameters

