may be analyzed using Spearman's rank correlation coefficient or other appropriate method.

More details for analyzing the secondary efficacy parameters will be given in the SAP.

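### The cortisol ANCOVA in section 11.4.2 omits hormonal contraceptive use, a factor the protocol itself ties to cortisol; this costs a little precision, not validity

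*Protocol*

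**What the plan says.** **Contraceptives are permitted.** Exclusion criterion 10 (section 6.2) bars "hormone preparations (e.g., thyroxine) with the exception of hormonal contraceptives". Section 7.6.1 carries the exemption through the trial: "hormone and homeopathic preparations (e.g., thyroxine) with the exception of contraceptives".

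**They enter the analysis plan once.** The subgroup list in section 11.3, repeated in the synopsis, contains "Cortisol response influenced by hormonal contraceptives". It gives no levels and no method.

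**Cortisol is a secondary efficacy variable in two forms** (section 11.4.2): "Resting state cortisol and other stress-related parameters in saliva" and "Serum cortisol levels and other stress-related parameters in response to the stress induction by CPT".

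**The model is stated.** Continuous secondary variables are compared with an "ANCOVA including treatment, the stratification factor sex, and the baseline value of continuous numeric parameters as covariate". Randomisation is stratified by sex only (section 11.2).

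**Status.** "Secondary analyses on efficacy will be exploratory in nature without adjustment for multiplicity". Section 11.4.2 ends with "More details for analyzing the secondary efficacy parameters will be given in the SAP", and section 11.3 allows the SAP to modify the protocol's plans.

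**The concern.** The protocol singles out one permitted background treatment as relevant to cortisol, and then gives it only a subgroup display. The covariates it names for the cortisol comparison leave that factor out.

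Sex does not stand in for it. Inclusion criterion 8 accepts hormonal and non-hormonal methods, and women who are not of childbearing potential need none, so the female stratum contains both users and non-users. The baseline cortisol value carries a stable contraceptive effect, but only in proportion to how well baseline predicts the later value. The rest stays in the residual.

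The subgroup cannot make up for this. It will be small, and it does nothing for the overall comparison. Its label also names a response rather than a grouping of patients, so it does not say who is compared with whom.

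At stake is some precision in the cortisol awakening, diurnal and Cold Pressor Test comparisons.

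**Working it through.** **The plan's own figure.** The protocol gives no power or precision for cortisol. Its sample size concerns sleep efficiency (section 11.1: difference 6.7, SD 10, two-sided 5%, power 80%). A two-sample t-test at 6.7/10 = 0.67 SD needs 35.96, so 36 per arm, or 72 in all, with power 0.8005; 72/0.9 = 80. This reproduces, and nothing below changes it. I use N = 72 for cortisol.

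**Step 1: how much a stable effect leaves behind, among women.** Assumptions: within-group variance 1, half the women users, users shifted by d SD equally at both visits, baseline-to-post correlation r.

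- Pooled slope without the covariate: b = (r + 0.25d²)/(1 + 0.25d²)
- Residual variance without it: (1 + 0.25d²)(1 − b²)
- Residual variance with it: 1 − r²

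At d = 1, r = 0.5: b = 0.75/1.25 = 0.60; 1.25 × 0.64 = 0.80 against 0.75, a reduction of 6.25%. Across the grid:

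| r | d = 0.5 | d = 1 | d = 1.5 |
|---|---|---|---|
| 0.3 | 3% | 10% | 16% |
| 0.5 | 2% | 6% | 11% |
| 0.7 | 1% | 3% | 6% |

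These percentages apply to women only. The trial's model includes men, so the effect on the treatment comparison is smaller.

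**Step 2: the whole sample.** I simulated the ANCOVA with and without the covariate. Assumptions: 72 patients, 60% women (43), 40% of women users (about 17 patients: 72 × 0.6 × 0.4 = 17.3), 1:1 allocation within sex, true treatment effect 0.5 SD, contraceptive shift equal at both visits, 60,000 runs per cell. Power without → with the covariate:

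| r | no contraceptive effect | shift 1 SD | shift 1.5 SD |
|---|---|---|---|
| 0.3 | 58.2% → 57.6% | 55.8% → 57.9% | 53.7% → 58.1% |
| 0.5 | 66.6% → 66.0% | 64.9% → 66.1% | 63.5% → 66.2% |
| 0.7 | 83.0% → 82.5% | 82.0% → 82.4% | 81.3% → 82.2% |

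The gain is about 0 to 4 points where there is a shift. The cost is under 1 point where there is none.

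**Step 3: validity.** A wider set of scenarios used r = 0.6, shifts of 0, 0.8 and 1.5 SD, some with a further 0.5 or 1.0 SD at the post visit only, and 4,000 runs each. The mean estimate stayed within about 0.01 SD of the truth, and the type I error lay between 0.045 and 0.053, with or without the covariate.

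**Step 4: what the subgroup can show.** Take 50–70% women and 20–60% use. Users then number between 72 × 0.5 × 0.2 = 7 and 72 × 0.7 × 0.6 = 30. The difference detectable within users at 80% power is 2.802 × √(4/n), with 2.802 = 1.960 + 0.842 and no baseline adjustment. That is 2.1 SD at n = 7.2 and 1.0 SD at n = 30.2. The subgroup is descriptive at best.

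**The case against.** The strongest reply is that nothing here is an error. Section 11.4.2 gives one generic model for every continuous secondary variable. It leaves further detail to an SAP that is not shown, and a covariate for one exploratory biomarker is ordinary SAP content. Most of this stands. It cannot be said that the plan has no other answer to contraceptive use. What remains is that the protocol is not silent: it names the covariates, and it places this factor among the subgroups.

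Several stronger readings are tempting, and the documents do not support them.

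- **Bias.** A reader might infer that users falling unevenly between arms distort the treatment estimate. Chance imbalance after randomisation is ordinary sampling error, already reflected in the standard error; step 3 shows no bias and no inflation.
- **A known effect.** The link to cortisol rests on a subgroup label. No section gives a direction or a size.
- **A mix created by amendment.** The change to inclusion criterion 8 widened the non-hormonal options, but users and non-users would be mixed anyway, since the criterion binds only women of childbearing potential and women up to 65 are eligible.
- **A large loss of power.** Losses of about 5 to 15 points do appear in simulation (for example 0.69 against 0.74, or 0.60 against 0.73), but only if contraceptives act more strongly at the post-treatment visit than at baseline. Nothing in the protocol suggests that.

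It is also fair that the low correlation of 0.3 may not apply. Section 9.1.2 takes five awakening samples a morning, and summaries over them may repeat better than single values. That moves the gain towards the lower end.

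**Conclusion.** The point holds as a minor improvement in efficiency. The protocol identifies a cortisol-related factor and permits it, but leaves it out of the stated cortisol model. The randomised comparison stays valid either way.

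The gain of about 0 to 4 power points rests on assumed values for the share of women, the share of users, the contraceptive shift, the correlation and the treatment effect, and on a shift that is the same at both visits. The 1% to 16% reductions in residual variance should not be quoted for the trial as a whole. These analyses are exploratory, so no confirmatory conclusion depends on the choice.

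**What to change.** In section 11.4.2 or the SAP, before database lock:

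1. For the salivary and serum cortisol variables only, add hormonal contraceptive use at baseline (yes/no; men = no) as a covariate beside treatment, sex and baseline value.
2. Reword the subgroup item as users versus non-users among women, and present it descriptively.
3. State which of the hormonal methods listed in inclusion criterion 8 count as use.

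The cost is one degree of freedom and a check of the data. Section 8.1 has concomitant medication documented at Screening but does not say that contraceptive type is recorded, so this should be confirmed. Naming the covariate in advance also avoids choosing it after unblinding. The primary analysis and the sample size need no change.

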11.3.1 Hypothesis

The null and alternative hypotheses for the comparison of Neurexan® versus Placebo can be formulated as follows:

$$H_0: \mu_N = \mu_P$$

$$H_A: \mu_N \neq \mu_P$$

H_0 : Null-hypothesis; H_A : Alternative Hypothesis; N: Neurexan®; P: Placebo
Treatment; μ : mean/ rate of population

The statistical null hypothesis of no difference between the 2 treatment groups (Neurexan® versus Placebo) in terms of the change of sleep efficiency measured by polysomnography from Baseline 2 to Visit 2 will be tested in a confirmatory sense based on the Intention-To-Treat (ITT) population. The test of the null hypothesis will be carried out two-sided. The null hypothesis will be rejected and the superiority of a treatment (Neurexan® or Placebo) will be claimed if the p-value will be equal or less than 0.05.

Sensitivity Analyses

Efficacy analyses will be performed with the ITT population and additionally with the Per-Protocol Population (PPP) to explore the robustness of the findings. The decision to perform a Per-Protocol (PP) analysis will be based on the number of patients excluded from the PPP. If this number is sufficiently low (less than 10% of the ITT population), no PP analysis will be performed. This decision will be taken prior to database lock.

Another sensitivity analysis will compare observed cases and data imputed with the last observation carried forward (LOCF) method (Section 11.4.3).

Further on, robustness analyses will include the Wilcoxon rank-sum test. Difference from baseline will be used, as appropriate.

11.3.2 Analysis Populations

Analyses will be based on the safety population, ITT population, and the Per-Protocol Population (PPP).

The screening population is defined as all patients who signed informed consent.

The safety population is defined as all patients who were randomized and received at least one dose of investigational medication. All safety analyses will be based on the treatment actually taken by the patient ('as treated').

The ITT population is defined as patients who were randomized and received at least one dose of investigational medication and had at least one post-dose assessment.

The Per-Protocol Population (PPP) is defined as all patients who received investigational treatment and fulfil the following criteria:

- The absence of any important major protocol deviations
- No technical difficulties during PSG
- Patients who were correctly stratified and received the correct treatment
- Sufficient treatment compliance of 80%-120%.

Treatment compliance will be defined via the amount of IMP that has been taken between first intake at Baseline 2/ second day and last intake at Visit 2/ first day in relation to the amount that should have been taken by a patient.

Protocol deviations will be collected during the entire trial and will be classified as minor or major at the BDRM. Protocol deviations that may affect the efficacy outcome of patients will be classified as major. The decision about major protocol deviations and assignments to populations will be taken in a blinded fashion and will be documented in the BDRM meeting minutes prior to unblinding of the trial.

11.4 Efficacy Analysis

11.4.1 Primary Efficacy

The primary efficacy variable for changes in sleep pattern will be sleep efficiency (SE) measured by polysomnography at Baseline 2 and Visit 2, calculated as the ratio of total sleep time (TST) to time in bed (TIB), as difference at Visit 2 to Baseline 2. Analysis of Covariance (ANCOVA) will be used to test the hypothesis of section 11.3.1. The model will include treatment and the stratification factor sex and will account for sleep efficiency at baseline as covariate. The test will be performed using a Type I error level of 5%, two-sided.

11.4.2 Secondary Efficacy

For all secondary variables, exploratory statistics comparing the 2 treatment groups will be performed. Difference from baseline will be used, as appropriate. Group comparisons of continuous numeric parameters will be tested using an ANCOVA including treatment, the stratification factor sex, and the baseline value of continuous numeric parameters as covariate; comparisons of dichotomous variables are specified by using the Fisher's Exact Test.

Secondary analyses on efficacy will be exploratory in nature without adjustment for multiplicity. All secondary analyses will be performed with two-sided hypotheses on superiority using a Type I error level of 5%.

Secondary efficacy variables are the following:

Polysomnography at Baseline 2 and Visit 2

- SOL
- WASO
- TST
- NWAK
- Latencies to S1, S2, S3, REM
- Arousal Index (Arl).

Biochemical parameters

- Resting state cortisol and other stress-related parameters in saliva
- Serum cortisol levels and other stress-related parameters in response to the stress induction by CPT
- Stress test induced inflammation parameters in blood serum.

Actigraphy

- Continuous in-home assessment of sleep
- Daytime activity.

Patient Questionnaires

- Subclinical Stress Symptom Questionnaire-25 (SSQ-25)
- Primary Appraisal Secondary Appraisal (PASA)
- Perceived Stress Scale-10 (PSS-10)
- Epworth Sleepiness Scale (ESS)
- Würzburg Fatigue Inventory (WEIMuS)
- Short Form-36 (SF-36v2)
- Insomnia Severity Index (ISI)
- Pittsburgh Sleep Quality Index (PSQI)
- Beck's Depression Inventory-II (BDI-II)
- Beck's Anxiety Inventory (BAI).

Sleep diary (adapted from DGSM) data: subjective SE, SOL, WASO, TST, NWAK

Continuous digital stress assessments

Neurexan® response

Exploratory Efficacy Variables

- EEG based vigilance fluctuations during resting state
- EEG based vigilance fluctuations during CPT
- EEG based asymmetry index during resting state
- EEG based vigilance fluctuations during CPT
- Regional changes in spectral characteristics of EEG during resting state
- Regional changes in spectral characteristics of EEG during CPT
- Cognitive performance in three attentional tasks

- PSG sleep parameters derived from the two adaptation nights at Baseline 1 and Visit 1.

Correlations between

- Changes in sleep parameters, stress parameters, and daytime performance
- Changes in sleep parameters, stress parameters, and inflammatory parameters

may be analyzed using Spearman's rank correlation coefficient or other appropriate method.

More details for analyzing the secondary efficacy parameters will be given in the SAP.

11.4.3 Handling of Missing Data

In general, for the patient data listings, no imputation of missing or incomplete dates will be applied. Data will be presented as collected.

The last observation carried forward (LOCF) method will impute missing data values using the last observation observed prior to the missing value, i.e., the last observation prior to the missing value is carried forward to the future missing time point(s). Only on-treatment, post-Baseline 2 observations will be used in the LOCF procedure, i.e., baseline values will not be used to impute values.

A more detailed description of the handling of missing data will be provided in the SAP.

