Abbreviations: AE - Adverse Event, BAI - Beck's Anxiety Inventory (paper PRO), BDI-II - Beck's Depression Inventory revision II (paper PRO), CBC - Complete Blood Count, CPT - Cold Pressor Test, CRP - C-reactive protein, DGSM - Deutsche Gesellschaft für Schlaforschung und Schlafmedizin, DHEA-S - dehydroepiandrosterone sulfate, DSM-5 - Diagnostic and Statistical Manual of Mental Disorders, 5th edition, EDA - Electrodermal Activity, EEG - electroencephalogram, EMAs - Ecological Momentary Assessments (used for daily stress assessment via **AMS-ePRO[®]**), EoT - End of Trial, (e)PRO - (electronic) Patient-Reported Outcome, ESR - Erythrocyte Sedimentation Rate, ESS - Epworth Sleepiness Scale (**AMS-ePRO[®]**), HR - Heart Rate, HRV - Heart Rate Variability, IMP - Investigational Medicinal Product, ISI - Insomnia Severity Index (**AMS-ePRO[®]**), min - minutes, ml - milliliters, PASA - Primary Appraisal Secondary Appraisal (**AMS-ePRO[®]**), PRO - Patient- Reported Outcome, PSG - polysomnography; PSQI - Pittsburgh Sleep Quality Index (paper PRO), PSS-10 - Perceived Stress Scale-10 (paper PRO), rsEEG - resting state electroencephalography, SF-36v2 - Short Form-36 version 2.0 (paper PRO), SSQ-25 - Subclinical Stress Symptom Questionnaire-25 (paper PRO), TAP - Test of Attentional Performance, WEIMuS - Würzburg Fatigue Inventory (paper PRO).

[^]Visit 1 may be performed on Day 12 +2 days. In any case, Visit 1 and Visit 2 will be performed on two consecutive days.

^{^^}Follow-up Visit may be performed on Day 28 +3 days.

◦ Demographics include sex, height and weight.

* Starting IMP treatment after having performed all Baseline 2 assessments and after randomization at midday Day 0 for 14 consecutive days (+ maximum 2 days allowance) until Visit 2 (Day 13).

◦◦ Sleep diary will be completed daily; starting at Screening Visit until End of Trial

Stress biomarkers in saliva: cortisol, alpha-amylase, dehydroepiandrosterone sulfate (DHEA-S) at 5 time points: after awakening from PSG nights at Baseline 1/ Day -1, Baseline 2/ Day 0, Visit 1/ Day 13 and Visit 2/ Day 14 collection of around 0.5 to 1 ml saliva at 0 minutes, 15 minutes, 30 minutes, 45 minutes, 60 minutes (5 time points) for the assessment of Cortisol Awakening Response (CAR) and additionally at Baseline 1/ Day -1 and Visit 1/ Day 13 diurnal profile of stress biomarkers by collecting saliva samples at 3-hourly intervals over 12 hours (4 time points) synchronized to the awakening time.

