5.3 Trial Duration

The First Patient First Visit (FPFV) was in June 2023. A total of 80 patients will be randomized within approximately 32 months. The Last Patient Last Visit (LPLV) is planned to be in January 2026.

The total trial duration for each patient is 37 to maximum 60 days (Table 3). Patients start with a Screening Visit 8 to 28 days prior to first investigational treatment (on Day 0), followed by two baseline visits for a PSG adaptation ('screening') night at Baseline 1/ Day -2 to -1 and the primary outcome relevant PSG night at Day -1 to Day 0, respectively. Patients are randomized to their investigational treatment after completion of visit Baseline 2 / Day 0. Patients will take their investigational treatment for 14 consecutive days (starting at Day 0 to Day 13). Patients will visit the investigational site at Day 12 +2 for a PSG adaptation night and at Day 13 +2 for the primary outcome relevant PSG night. On Day 28 +3 a Follow-up Visit will take place to collect paper-based patient-reported outcome data of BAI, PSQI, PSS-10, SF-36v2 and SSQ-25 questionnaires and the End of Trial (EoT) documentation is to be completed.

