- Urine collection for test on drugs in the evening at Day 12 (section 9.1.11)
- Breath alcohol test in the evening at Day 12 (section 9.1.11)
- PSG night, again for adaptation to the unfamiliar sleep lab environment between Day 12 and Day 13 (section 9.1.1)
- Collection of 0.5 to 1 ml saliva to measure cortisol, DHEA-S and alpha-amylase at awakening (0 minutes), and at 15 minutes, 30 minutes, 45 minutes, 60 minutes, 3 hours, 6 hours, 9 hours and 12 hours after awakening at Day 13 (section 9.1.2)
- Neuropsychological tests (TAP) at Day 13 (section 9.1.10)

- Resting state EEG, resting state HR and HRV to measure daytime performance at Day 13 (section 9.1.3)
- CPT around 12:00 including subjective pain and stress rating, heart rate and associated HRV measures, electrodermal activity, and EEG at Day 13 (section 9.1.7)
- Collection of approximately 12.5 ml blood for measuring cortisol, DHEA-S, adrenaline, noradrenaline, inflammation markers (IL-6 and TNF- α) prior to CPT, 20 minutes and 50 minutes after CPT at Day 13 (section 9.1.8)
- Completion of the following questionnaires: ESS, ISI, PASA (**AMS-ePRO[®]**); BDI-II and WEIMuS (both paper-based; section 9.1.14)
- Adverse events at Day 12 (section 9.2.1)
- Changes in concomitant medication at Day 12
- Complete sleep diary and stress assessment (in **AMS-ePRO[®]**).

At **Visit 2** (Day 13 to Day 14; + 2 days but on the next day after Visit 1) patients will stay at the site for a second night for PSG. After awakening (Day 14) resting state stress parameters in saliva are to be collected (at 5 time points).

The following procedures will be performed:

- Urine collection for test on drugs in the evening at Day 13 (section 9.1.11)
- Breath alcohol test in the evening at Day 13 (section 9.1.11)
- Last IMP intake in the night of Day 13 prior to sleep
- PSG recording to measure SOL, WASO, TST, NWAK, and arousal indices during sleep in the night between Day 13 and Day 14 (section 9.1.1)
- Collection of 0.5 to 1 ml saliva to measure cortisol, DHEA-S and alpha-amylase at awakening (0 minutes), and at 15 minutes, 30 minutes, 45 minutes, 60 minutes after awakening at Day 14 (section 9.1.2)
- Adverse events at Day 13 and Day 14 (section 9.2.1)
- Changes in concomitant medication at Day 13 and Day 14
- Complete sleep diary and stress assessment (in **AMS-ePRO[®]**)
- Return of IMP.

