9.1 Efficacy Parameters/ Assessments

9.1.1 Polysomnography (PSG)

PSG is the gold standard for the objective assessment of sleep parameters. The Interdisciplinary Center for Sleep and Ventilatory Medicine at the Jena University Hospital is certified by the German Sleep Medicine Society (DGSM) and follows the recommended diagnostic and therapeutic standards.

During PSG brain activity (electroencephalogram, EEG), eye movement (electro-oculogram), muscle activity (electromyogram) and cardiac activity (electrocardiogram) as well as respiratory parameters (airflow, respiratory effort, and oximetry) will be recorded.

Sleep efficiency (SE) is calculated as the ratio of total sleep time (TST) to time in bed (TIB) (i.e., both sleeping and attempting to fall asleep or fall back asleep). Sleep onset latency (SOL) is the time in minutes from 'lights out' to the first sequence scored as sleep. The sleep time in minutes on each sleep phase S1, S2, S3 and rapid eye movement (REM) are recorded. Total sleep time (TST) is the total amount of sleep time summarized of different sleep stages during the total recording time (time in bed, TIB). Periods of wakefulness occurring after the onset of sleep are defined as wake after sleep onset (WASO). The number of awakenings (NWAK) are counted.

Patients will spend 2 nights each onsite in the sleep laboratory for PSG adaptation (Baseline 1 and Visit 1) and for PSG (Baseline 2 and Visit 2). PSG measurements recorded during adaptation nights will not be used for primary and secondary endpoints but analyzed on exploratory basis only.

Daytime napping is not allowed before and after PSG nights. With urine and breath alcohol tests, patients will be screened for drug abuse and alcohol at Screening Visit and prior to PSG nights at Baseline 1, Baseline 2, Visit 1 and Visit 2.

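### For polysomnography endpoints, the planned observed-case versus LOCF comparison has no value to carry forward, so it cannot test robustness to missing Visit 2 sleep efficiency

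*Protocol*

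**What the plan says.** Section 11.3.1 sets out the confirmatory test of SE change in the ITT population and then lists the sensitivity analyses. One is a per-protocol analysis, with a skip rule: "If this number is sufficiently low (less than 10% of the ITT population), no PP analysis will be performed". Another concerns missing data: "Another sensitivity analysis will compare observed cases and data imputed with the last observation carried forward (LOCF) method". The last is a Wilcoxon rank-sum test.

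Section 11.4.3 fixes which values LOCF may use: "Only on-treatment, post-Baseline 2 observations will be used in the LOCF procedure, i.e., baseline values will not be used to impute values". It leaves further detail to the SAP.

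Section 11.4.1 defines the primary variable from "sleep efficiency (SE) measured by polysomnography at Baseline 2 and Visit 2". Section 11.4.2 ties the secondary PSG variables to the same two nights and lists PSG parameters from the adaptation nights separately, as exploratory. Section 11.3 defines the PSG baseline as the Baseline 2 night.

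Section 9.1.1 governs the adaptation nights: "PSG measurements recorded during adaptation nights will not be used for primary and secondary endpoints but analyzed on exploratory basis only". Visit 1 is such a night. Section 8.1 describes it as a "PSG night, again for adaptation to the unfamiliar sleep lab environment between Day 12 and Day 13", and section 5.3 says patients attend during treatment "for a PSG adaptation night and at Day 13 +2 for the primary outcome relevant PSG night". The footnote in section 2.2 adds: "In any case, Visit 1 and Visit 2 will be performed on two consecutive days".

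**The concern.** LOCF needs at least one admissible value between baseline and the missing visit. For PSG, the donor rule in 11.4.3 and the exclusion of adaptation nights in 9.1.1 appear to leave none. The comparison would then return the observed-case result whatever the missing Visit 2 values might have been, and that agreement could be reported as robustness.

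This matters because missing Visit 2 SE within the ITT population is foreseeable:

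- A 10% dropout rate is planned (11.1), and drop-outs are not replaced (6.3).
- ITT membership needs one dose and one post-dose assessment (11.3.2), not a Visit 2 PSG. On that wording a daily diary entry (9.1.9) would be enough.
- Technical difficulty during PSG removes a patient only from the per-protocol population (11.3.2).

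The other two checks in 11.3.1 do not cover the gap. The per-protocol analysis removes patients rather than accounting for missing values, and it may be skipped. The Wilcoxon test addresses the distribution of the outcome.

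**Working it through.** **The plan's own figures.** Inputs from 11.1: difference 6.7, SD 10, two-sided alpha 5%, 80% power, 10% dropout. A two-sample t-test with 36 per arm has power 0.8005, so 72 evaluable patients reproduces. Inflation: 72 / 0.9 = 80. Expected losses: 80 − 72 = 8.

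**Candidate donors for a missing Visit 2 PSG.** Nights from 8.1 and 9.1.1, tested against the two rules:

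| PSG night | On-treatment and post-Baseline 2 (11.4.3) | Not an adaptation night (9.1.1) | Admissible |
|---|---|---|---|
| Baseline 1 (Day −2 to −1) | no | no | no |
| Baseline 2 (Day −1 to 0) | no | yes | no |
| Visit 1 (Day 12 to 13) | yes | no | no |

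Admissible donors: 0 of 3. Visit 2 is itself the night to be imputed.

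**Consequence for the comparison.** Assume all 8 expected losses lack a Visit 2 PSG.

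- Observed-case n = 80 − 8 = 72
- Values filled by LOCF = 0
- LOCF n = 72 + 0 = 72
- Difference between the two results = 0

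The zero does not depend on the number 8, because with no donor the two data sets are identical for any number missing. The same applies to SOL, WASO, TST, NWAK, the latencies to S1, S2, S3 and REM, and the arousal index: 4 + 4 + 1 = 9 secondary PSG variables.

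**If Visit 1 were allowed as donor.** Between 0 and 8 of the 8 could be filled, depending on when patients are lost. Visits 1 and 2 are consecutive, so only patients lost after the Visit 1 night, or whose Visit 2 recording fails, would gain a value. An adaptation night would then be compared with a baseline taken after adaptation.

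**Per-protocol skip rule.** Taking 80 ITT patients, fewer than 10% means fewer than 8. The analysis is not run with 7 or fewer exclusions.

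**What a working check would respond to (illustration only).** Assume an observed difference of 6.7, 40 patients per arm, and all 8 missing patients in the ITT population. If each missing patient is given the placebo mean, the difference becomes 6.7 × (observed Neurexan patients / 40):

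| Missing in Neurexan arm | Placebo-reference difference | Shift from LOCF versus observed cases |
|---|---|---|
| 0 | 6.7 × 40/40 = 6.70 | 0 |
| 4 | 6.7 × 36/40 = 6.03 | 0 |
| 8 | 6.7 × 32/40 = 5.36 | 0 |

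The split between arms is an assumption. The figures are not an estimate of bias in the primary result.

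**The case against.** The strongest counter-reading is that 11.4.3 taken literally admits Visit 1: it is on treatment, after Baseline 2, and the last value before Visit 2. Section 9.1.1 allows exploratory use of adaptation nights, and a sensitivity analysis that does not decide the primary test might be placed there. Such a donor would have some use. Drug and alcohol tests are repeated on the evening of Day 13, after the Visit 1 night, and a positive result is a possible reason for withdrawal (6.3, 8.1). Those patients, and failed Visit 2 recordings, could be filled. This reading does not rescue the plan. An imputed Visit 2 SE still puts an adaptation night into the primary endpoint, and 9.1.1 makes no exception for imputation. Patients lost before Visit 1 remain unfilled.

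A second objection is that missing-data detail belongs to the SAP, which was not available for this review. That is fair for the choice of any additional method. It does not help here, because the LOCF comparison, the donor rule and the exclusion of adaptation nights are all fixed in the protocol. A SAP that follows them inherits an empty comparison.

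Third, the LOCF sentence does not name SE, and LOCF does work for repeated on-treatment data such as the diary. Both points stand, and the finding is limited to PSG variables. But the sentence sits under the confirmatory SE hypothesis and does not exclude PSG.

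It is also true that the placebo-reference figures belong to an analysis the protocol does not plan, and that some of the 8 losses may fall outside the ITT population. They serve only as an illustration.

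**Conclusion.** The concern holds. Under the protocol's own rules, the observed-case versus LOCF comparison is identical by construction for SE and the 9 secondary PSG variables: no value is filled, and the difference is exactly 0 for any number of missing Visit 2 nights. The alternative reading replaces an empty check with a conflict between 11.4.3 and 9.1.1, and it helps only patients who completed the Visit 1 night.

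The conclusion rests on reading 9.1.1 as covering imputation of an endpoint as well as its direct analysis. The figure of 8 missing is the planning assumption and assumes that every loss lacks a Visit 2 PSG; the zero does not depend on it.

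The consequence is limited but real: the only missing-data check named for the one confirmatory test gives no information on robustness to missing data. The primary endpoint, its ANCOVA and the sample size are unaffected. This should be fixed.

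**What to change.** Before database lock and unblinding:

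1. State that LOCF is not applied to PSG variables (11.3.1 and 11.4.3). Keep it, if wanted, for repeated on-treatment measures such as the diary.
2. For SE, specify a sensitivity analysis in the ITT population that can respond to missing Visit 2 values. One option is multiple imputation from arm, Baseline 2 SE and sex, with a delta/tipping-point or placebo-reference version.
3. If Visit 1 SE is to serve as an auxiliary predictor, permit that use in 9.1.1.
4. Leave the primary ANCOVA unchanged.

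Cost: SAP text and slightly more analysis work, with no new visits or data. Section 11.3 lets the SAP modify the planned analyses and requires an amendment only for major changes to the primary endpoint or its analysis, which stay as they are. Correcting the protocol sentences as well would be cleaner, but a formal amendment goes through the approval process in 12.5.
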